#### Analysis of Additional Secondary Outcomes

Secondary objectives with respect to pulmonary hemodynamics (i.e., PAP, cardiac output, RAP PAWP), quality of life, and other continuous secondary outcomes will be analyzed using an approach similar to that used for analysis of our primary outcome of 6MWD. The combined endpoint of death or clinical worsening of pulmonary arterial hypertension up to 12 months will be described using Kaplan-Meier plots and compared across the 3 study arms using log-rank tests. Chi square test statistics and relative risks with 95% confidence intervals will be used to determine the effect of four doses of treatment on the combined endpoint at 6 months (Arm 1 vs. Arms 2 and 3). The combined endpoint at 12 months in Arm 3 will be described using 95% confidence interval and compared to historical event rates.

---

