**Secondary objectives:**

1. To compare the sustained effect of delivery of 4 vs. 8 doses of the cell therapy product on 6MWD at 12 months (i.e. Arm 2 vs. Arm 3)
2. To assess durability of any improvement in 6MWD at 3 vs. 9 months post last dose of cell therapy product (Arm 2 only)
3. To determine the incremental effect of delivery of 8 vs. 4 doses of the cell therapy product on 6MWD at 6 and 12 months (Arm 3 only)
4. To assess the cumulative effect of 4 doses of the cell therapy product on pulmonary vascular resistance at 6 months (Arms 2 and 3 vs. Arm 1)
5. To compare the sustained effect of delivery of 4 vs. 8 doses of the cell therapy product on pulmonary vascular resistance at 12 months (i.e. Arm 2 vs. Arm 3)
6. To assess durability of any improvement in pulmonary vascular resistance at 3 vs. 9 months post last dose of cell therapy product (Arm 2 only)
7. To determine the incremental effect of delivery of 8 vs. 4 doses of the cell therapy product on pulmonary vascular resistance at 6 and 12 months (Arm 3 only)
8. To assess effect of cell therapy on Quality of Life measured by the SF-36 at 6 months (Arms 2 and 3 vs. Arm 1)
9. To compare the sustained effect of delivery of 4 vs. 8 doses of the cell therapy product on Quality of Life measured by the SF-36 at 12 months (i.e. Arm 2 vs. Arm 3)
10. To assess the effect of cell therapy on a combined endpoint of death, or clinical worsening of pulmonary arterial hypertension at 6 and 12 months
11. To assess effect of cell therapy on measures of RV function by echocardiography at 6 and 12 months
12. To assess effect of cell therapy on RV function by Magnetic Resonance Imaging (MRI) at sites where this is available in patients with no contraindications for MRI (i.e. prostacyclin infusion pump, claustrophobia) at 6 and 12 months

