***The primary effect measure is at the 6 month time point.***

However, the study continues beyond 6 months in order to address a number of important secondary endpoints. ***Importantly, the blind will continue over the entire 12 month period of the study.***

- **Course 2:** In the second 6 month period, the study treatments will be altered to address specific questions about the timing and durability of this cell therapy:
  - Arm 1: Participants previously receiving placebo will now receive a course of 4 cell therapy treatments allowing all participants in this trial to have the opportunity to be given the active study product.

- Arm 2: Participants previously receiving EPCs will now receive the placebo study product to allow an assessment of the durability of any potential benefit of the cell therapy provided in Course 1 over the remaining 6 months of the study.
- Arm 3: Participants previously receiving EPCs will now receive a second course of cell therapy treatments, for a total of 8 doses of eNOS-transfected EPCs. This Arm will determine whether 8 repeated doses of the cell therapy product provides a greater incremental benefit than 4 doses.

After the 12-month treatment and follow-up period is complete, the study will be converted to a long-term follow-up registry extending to 10 years.

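### For death or clinical worsening, the 12-month half of objective 10 has no named randomised contrast: the planned analyses compare treatment sequences and set Arm 3 against unsourced historical rates, though Arm 2 is a concurrent blinded comparator for the second course

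*SAP*

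**What the plan says.** Objective 10 (SAP Secondary objectives; Protocol 2.2) is to assess the "effect of cell therapy on a combined endpoint of death, or clinical worsening of pulmonary arterial hypertension at 6 and 12 months". It names no arms.

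SAP 5.2, Analysis of Additional Secondary Outcomes (same text in Protocol 11.8), plans three analyses:

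- **To 12 months:** Kaplan-Meier plots, "compared across the 3 study arms using log-rank tests".
- **At 6 months:** chi-square and relative risk, "used to determine the effect of four doses of treatment on the combined endpoint at 6 months (Arm 1 vs. Arms 2 and 3").
- **At 12 months, Arm 3 alone:** "The combined endpoint at 12 months in Arm 3 will be described using 95% confidence interval and compared to historical event rates".

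Neither document gives a source, value, population or endpoint definition for the historical rates.

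SAP 2.1 says of Arm 3: "This Arm will determine whether 8 repeated doses of the cell therapy product provides a greater incremental benefit than 4 doses". It also states that "the blind will continue over the entire 12 month period of the study". Other objectives name the matching contrast at 12 months. Objective 1 does so for 6MWD, objective 5 "on pulmonary vascular resistance at 12 months (i.e. Arm 2 vs. Arm 3") and objective 9 for "Quality of Life measured by the SF-36 at 12 months (i.e. Arm 2 vs. Arm 3").

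**The concern.** From Month 6 no arm is on its original contrast with placebo: Arm 1 moves to cells, Arm 2 moves to placebo and Arm 3 continues on cells. A comparison of the three curves over 12 months therefore mixes the effect of cells, their timing and any carry-over. The only other 12-month statement is non-randomised, although the design contains a randomised, blinded comparator for the second course.

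At stake is what may be claimed about clinical events after 12 months. As written, the choice of pairwise test, and the choice of historical rate against which Arm 3 is judged, could both be made after unblinding.

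**Working it through.** **1. Contrasts named, by endpoint**

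| Endpoint | Month 6 | Month 12 |
|---|---|---|
| 6MWD | Arms 2+3 vs 1 | Arm 2 vs 3 (objective 1) |
| PVR | Arms 2+3 vs 1 (objective 4) | Arm 2 vs 3 (objective 5) |
| SF-36 | Arms 2+3 vs 1 (objective 8) | Arm 2 vs 3 (objective 9) |
| Death/worsening | Arms 2+3 vs 1 (chi-square, RR) | 3-arm log-rank; Arm 3 vs historical |

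**2. What the arms can estimate.** Treatment in Months 0-6 / 6-12 is placebo/cells (Arm 1), cells/placebo (Arm 2) and cells/cells (Arm 3). Arm 3 vs Arm 2 isolates the second course (8 vs 4 doses). No pair gives cells against none over 12 months.

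**3. The plan's own figure.** The documents give no event rate, hazard ratio or power for this endpoint. The only sizing figure is for 6MWD. With SD 85 and correlation 0.80 (SAP 2.3), the residual SD is 85 × √(1 − 0.80²) = 51.0. With 13 vs 26 participants, a 50 m difference and 35 df, the noncentral t gives 80.1% power, as stated. The same SD and correlation are used in step 4.

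**4. Dependence on visit schedule.** One component is a 6MWD fall of 15% or more (SAP 5.1), with no confirmation required. Month 0 is the baseline (Protocol Appendix D), and ten later visits measure 6MWD, five of them by Month 6. Assume no true change and mean μ. A fall means Y₁ − 0.85·Y₀ ≤ 0. This difference has mean 0.15μ and SD 85 × √(1 + 0.85² − 2 × 0.85 × 0.80) = 85 × √0.3625 = 51.2. The one-visit probability is Φ(−0.15μ/51.2):

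- μ = 250: Φ(−0.73) = 23%
- μ = 300: Φ(−0.88) = 19%
- μ = 350: Φ(−1.03) = 15%

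Simulating 400,000 walkers, with correlation 0.80 between all visits and baseline held to 125-440 m, gives for μ = 250/300/350:

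- one visit: 23/19/15%
- five visits: 56/49/41%
- ten visits: 70/62/54%

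A historical rate from another visit schedule is therefore not comparable.

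**5. Precision of Arm 3 alone.** As an example, 3 events in 15 has an exact (Clopper-Pearson) 95% CI of 4.3% to 48.1%.

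**6. Precision of Arm 3 vs Arm 2.** Assumed, and not counting walk-test noise: control 6-month risk p, on-treatment HR h, 15 per arm, and Arm 2's effect either lost or kept after Month 6. The proportion event-free at Month 6 is S = (1 − p)^h in both arms. Expected events in Months 6-12 are 15·S·(1 − S) in Arm 3. In Arm 2 they are 15·S·p if the effect is lost, or the same as Arm 3 if it is kept. The 12-month totals add 15·(1 − S) per arm. The CI factor either side of the HR is exp(1.96 × √(1/e₂ + 1/e₃)).

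| p / h | Arm 2 effect | Months 6-12: events Arm 2, Arm 3 (factor) | Months 0-12: events Arm 2, Arm 3 (factor) |
|---|---|---|---|
| 20% / 0.5 | lost | 2.68, 1.42 (7.7) | 4.27, 3.00 (4.4) |
| 20% / 0.5 | kept | 1.42, 1.42 (10.3) | 3.00, 3.00 (5.0) |
| 50% / 0.5 | lost | 5.30, 3.11 (4.1) | 9.70, 7.50 (2.6) |
| 50% / 0.5 | kept | 3.11, 3.11 (4.8) | 7.50, 7.50 (2.8) |
| 40% / 0.35 | lost | 5.02, 2.05 (5.1) | 7.47, 4.51 (3.2) |
| 40% / 0.35 | kept | 2.05, 2.05 (6.9) | 4.51, 4.51 (3.7) |

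With the plan's 10% attrition (13.5 per arm), the Months 6-12 factors become 4.4 to 11.6. The 0-12 month intervals are narrower, but the estimate is pulled towards 1 by six months of identical treatment. If the effect is lost, simulated power in the three settings is 8%, 10% and 17% for 0-12 months, and 8%, 16-17% and 25-26% for Months 6-12.

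**The case against.** **Pairwise tests may be intended.** The plural in the log-rank sentence could cover Arm 3 vs Arm 2. That is a fair reading, but none is named, and this endpoint has no counterpart to objectives 1, 5 and 9.

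**The sequences are fully described.** SAP 2.1 sets out each arm's treatment and says that Course 2 addresses timing and durability. The plan never presents the 12-month curves as cells against placebo, nor does it pool Arms 2 and 3 beyond Month 6. A reader might infer that it will report a diluted pooled 12-month hazard ratio; the documents contain no such analysis. What stands is that objective 10 asks for an effect of cell therapy at 12 months and no listed analysis supplies one.

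**The historical comparison is only descriptive.** Arm 3 is indeed to be described with a CI. It is then compared with rates that have no source or definition, and step 4 shows how much the definition and schedule matter.

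**The replacement gains little power.** Correct. The gain is a randomised, interpretable question. The historical comparison relies on the same 15 Arm 3 participants without randomisation.

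**A landmark at Month 6 leaves the intention-to-treat set.** Correct, so it should only support an all-randomised estimate. It remains balanced in expectation, because Arms 2 and 3 have identical blinded treatment until Month 6 dosing, which follows all other procedures of that visit (Protocol Appendix H).

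**Conclusion.** The point holds for the 12-month half of objective 10 only. The Month 6 test is sound and already planned. The three-arm log-rank is a valid test of randomised sequences, and type I error is not inflated. The endpoint is secondary, unpowered and without multiplicity adjustment (SAP 3.1), and the primary analysis is untouched. The plan should be changed, but nothing central depends on it.

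A reader might infer that Arms 1 and 2 must have equal 12-month risk whatever the cells do, so that the curves always hide an effect. The documents do not support that. It needs both no carry-over and the same background hazard in each half. With an assumed 40% first-half risk, HR 0.35 and no carry-over, equal hazards give 50/50/30% in Arms 1/2/3. Halving the second-half background hazard gives 45/35/24%, and doubling it gives 58/70/42%. The weaker statement is enough: the curves do not isolate cells against placebo.

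The visit-schedule figures rest on the plan's SD and correlation, an assumed mean of 250-350 m, equal correlation between visits and no true change. The event counts and CI widths rest on assumed risks and hazard ratios that leave out walk-test noise. That noise alone would give 41-56% an event by Month 6, so only about 7-9 of 15 per arm might enter the landmark, against 11-13 under the assumed rates.

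**What to change.** In SAP 5.2 and Protocol 11.8:

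1. Make the 12-month inference a named Arm 3 vs Arm 2 contrast (8 vs 4 doses): a hazard ratio with 95% CI in all randomised participants over Months 0-12. Add a supportive landmark analysis of Months 6-12 in those event-free at Month 6. State that both are estimates, not powered tests.
2. Label the three-arm Kaplan-Meier plots and log-rank as a comparison of treatment sequences.
3. Drop the historical comparison, or keep it as descriptive only, with source, endpoint definition and visit schedule fixed before unblinding.

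In the objectives of both documents:

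4. Align objective 10 so that its 12-month part names Arm 2 vs Arm 3, since no arm stays on placebo for 12 months.

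The cost is wording; no new data or visits are needed. The price is imprecision: about 3 to 8 landmark events under the assumed rates, with a CI 4- to 12-fold either side, and an all-randomised contrast diluted by the identical first six months. The trial will still have no concurrent control for 8 doses against none.

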## 2.2 Randomization and Blinding

### Randomization

Eligible participants will be randomized only following the completion of a satisfactory apheresis collection and receipt of the sample by the CMF. CMF personnel who have been trained by the sponsor to perform randomizations will access the SAPPHIRE web-based randomization system available from the Ottawa Methods Centre (OMC) located at OHRI. Personnel requiring access to this system will receive individual confidential login accounts from Data Management Services at the OMC.

After accessing the SAPPHIRE randomization system, the web-page will prompt the user to confirm participant eligibility by completing an electronic randomization case report form. Once completed, the web-based program will generate a randomization number on the screen. The requesting CMF user will print the screenshot containing the randomization number and will file it in the CMF participant binder. A copy will then be scanned and emailed to the study site for placement in the participant's study file.

Randomization to treatment allocation will be performed using a randomly permuted block design of fixed sizes of 3, stratified based on the average of the two screening 6MWD test results ( $\leq 300$  m vs.  $> 300$ m) and type of PAH (scleroderma associated PAH vs. all other eligible PAH types). Since our sample size for this late phase trial is relatively small, stratification is used to promote balance across the arms with respect to the baseline measure of the primary outcome, as well as type of PAH, an important prognostic factor for response to therapy. In particular, scleroderma associated PAH tends to progress more rapidly and show less favourable response to PAH-specific therapies. The allocation sequence will be generated using a computer-generated algorithm operated by the unblinded statistician for the trial located at the OMC. The study sponsor/CRO will monitor all randomizations throughout the conduct of the trial. The OMC will also generate a blinded email notification to the study site, study sponsor, and the CMF as confirmation of successful randomization. The CMF will subsequently receive a notification with the unblinded treatment allocation in order to proceed with manufacturing of the participant's study product.

Blinding

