## 2.3 Sample Size

A total sample size of 39 participants (13 per arm) in an analysis of covariance using a planned comparison between the average of the two treatment arms versus control achieves 80% power to detect a minimally important mean difference of **50 meters** in the primary outcome (6MWD) using an F-test with a two-sided 5% significance level. The SAS procedure GLMPOWER was used to conduct the calculation (SAS Institute Inc. 2008. SAS/STAT® 9.2. User’s Guide. Cary, NC: SAS Institute Inc). The common standard deviation is assumed to be 85 and the correlation between baseline and 6 months is 0.80. These estimates are similar to those observed in our PHACeT trial where the standard deviation was 80 meters and the correlation between baseline and 6 month was 0.86. To account for 10% potential attrition, we will enroll and randomize 45 subjects (15 allocated to each arm).

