#### Analysis of Primary Outcome (6MWD at 6 months)

The primary analysis of our primary outcome, 6MWD assessed at baseline, one, two, three, four and six months, will use a general linear model with time (coded as a categorical variable) and group by time interaction as fixed covariates. As recommended for efficient analyses of longitudinal randomized controlled trials, baseline differences between the arms will be constrained through exclusion of the main effect for group. In addition to providing the unadjusted effect, we will adjust our estimate for the stratification factors (6MWD  $\leq 300$ m vs.  $> 300$ m and scleroderma APAH vs. all other eligible PAH categories), as well as age, gender and

baseline medication use (PDEVi and sGC stimulators vs. all other PAH-specific medications). The model will be estimated using Restricted Maximum Likelihood (REML), and degrees of freedom will be computed using the Kenward-Roger approach. Suitable covariance structures to account for correlation among repeated measures over time will be identified using likelihood ratio tests and information criteria (AIC and BIC). For the primary endpoint, the adjusted least square mean difference between the average of the two active treatment arms (Arms 2 and 3) versus placebo (Arm 1) at 6 months, together with 95% confidence interval, will be obtained and assessed at the two-sided 5% level of significance. Additional exploratory pairwise comparisons of least square mean differences at one, two, three, and four months will be conducted.

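### The death or clinical-worsening tests ignore the randomisation strata; if those strata predict the composite, the 6-month chi-square is conservative and loses a little power

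*SAP*

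**What the plan says.** **Randomisation.** SAP 2.2 (Protocol 5 is the same): "Randomization to treatment allocation will be performed using a randomly permuted block design of fixed sizes of 3, stratified based on the average". The averaged quantity is the screening 6MWD, cut at 300 m, and the other factor is scleroderma against other PAH. That makes four strata. The reason given for the second factor is "as well as type of PAH, an important prognostic factor for response to therapy", and the text adds that "scleroderma associated PAH tends to progress more rapidly and show less favourable response to PAH-specific therapies". The first factor is justified only as the baseline measure of the primary outcome.

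**Primary analysis.** For 6MWD, SAP 5.2 and Protocol 11.4 say "we will adjust our estimate for the stratification factors".

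**Composite.** SAP 5.2, Analysis of Additional Secondary Outcomes (Protocol 11.8 is the same): "Chi square test statistics and relative risks with 95% confidence intervals will be used to determine the effect of four doses of treatment". The endpoint is death or clinical worsening by month 6, with Arm 1 set against Arms 2 and 3 together. Over the full 12 months the three arms are compared by log-rank tests. No stratified or adjusted form of either test is given. The sentence that carries the primary model over to other outcomes covers continuous ones only.

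No event rate, stratum effect or power is stated for the composite.

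**The concern.** Blocking within strata forces the arms to be nearly balanced on the stratification factors. If those factors predict the outcome, the treatment comparison varies less from trial to trial than an unstratified test assumes. The test then uses too large a null variance, rejects less often than its nominal 5%, and gives up power.

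The plan's own wording makes this plausible. PAH type is said to affect the speed of progression, and the composite measures progression (death, hospitalisation for disease progression, a 6MWD fall of at least 15%, worse WHO class). The plan uses the strata in the design and in the primary model, then drops them, without a reason, for death or clinical worsening. About 15 patients are compared with 30, so there is little power to spare.

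**Working it through.** **1. The plan's own figure.** The only power statement is for 6MWD: the design "achieves 80% power to detect a minimally important mean difference" of 50 m "using an F-test with a two-sided 5% significance level".
- Residual SD = 85 × √(1 − 0.80²) = 51.0.
- Standard error for 26 against 13 = 51.0 × √(1/13 + 1/26) = 17.32.
- Noncentrality = 50 / 17.32 = 2.89. On 35 degrees of freedom, power is 0.801.
- 39 / 0.9 = 43.3, rounded up to 44, or 45 in multiples of three.

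The figure reproduces, but it says nothing about the composite.

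**2. The mechanism by hand.** Let p be the overall risk and p_k the risk in stratum k. With balanced strata, the true null variance divided by the one that the chi-square uses is about 1 − Var(p_k) / [p(1 − p)]. Suppose that only scleroderma is prognostic, with an assumed share of 30% and assumed risks of 55% against 30% (odds ratio (0.55/0.45) / (0.30/0.70) = 2.9).
- p = 0.7 × 0.30 + 0.3 × 0.55 = 0.375, so p(1 − p) = 0.234.
- Var(p_k) = 0.7 × 0.3 × 0.25² = 0.0131.
- Ratio = 1 − 0.0131/0.234 = 0.944.
- Real size = 2 × [1 − Φ(1.96/√0.944)] = 2 × [1 − Φ(2.017)] = 4.4%.

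Simulation of this case gives 4.5% for the chi-square and 4.8% for CMH, with a power gain of about 1 point.

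**3. Simulation over a range.**
- From the documents: N = 45, four strata, blocks of 3 with one placebo patient per block, two-sided 5%.
- Assumed: half of patients at or below 300 m; scleroderma share 20% or 40%; placebo risk 30% or 50%; treatment odds ratio 1, 0.4 or 0.2; the same odds ratio for each stratification factor on the composite.
- 40,000 trials per setting. The standard error of a size near 5% is √(0.05 × 0.95/40,000) = 0.1 point.

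| Odds ratio of each factor | Chi-square size | CMH size | Power, CMH minus chi-square |
|---|---|---|---|
| 1 | 4.9–5.2% | 4.8–5.0% | −1.1 to −0.4 points |
| 1.5 | 4.8–5.2% | 4.7–5.0% | −0.7 to +0.1 |
| 2 | 4.2–5.1% | 4.7–5.0% | 0 to +0.7 |
| 3 | 3.6–4.3% | 4.8–5.0% | +1.6 to +2.9 |
| 5 | 2.7–3.4% | 4.7–5.0% | +3.7 to +7.0 |

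**4. Absolute power.** At treatment odds ratio 0.4 (for example 30% against about 15%), power is 16% to 30% over both tests and all settings. At 0.2 it is 40% to 66%.

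**5. Without any stratum effect.** Exact enumeration of the chi-square at 15 against 30 gives a size of 3.6%, 5.0%, 5.4%, 4.8% and 4.6% at risks of 10% to 50% in steps of 10. The small excess at 30% comes from discreteness, not from ignoring strata.

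**6. Cost of CMH when strata do not matter.** About 0.6 points of power at a common risk of 35% and about 1.5 points at 10%.

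The log-rank test was not simulated. The same mechanism applies to it, but no size is claimed.

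**The case against.** The strongest reply is that the harm is conditional and small.

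- **The condition is not documented.** A reader might infer that the chi-square certainly runs below 5% and loses several points of power. The documents do not support that: they give no stratum effect on the composite, and at odds ratios up to 2 almost nothing is lost.
- **The large losses need 6MWD to be strongly prognostic too.** Only PAH type is called prognostic, and with scleroderma alone at an odds ratio of about 2.9 the gain is about 1 point. Two components, the 15% walk decline and worse WHO class, are changes from the patient's own status, so a strong 6MWD effect cannot be presumed. A 15% fall is fewer metres for a poorer walker (18.75 m from 125 m, 66 m from 440 m), but the documents do not say whether or in which direction this changes risk.
- **The error is on the safe side.** The endpoint is secondary, without multiplicity control, and stratifying would not rescue a comparison with so few patients.
- **CMH has its own cost.** With 30% scleroderma and an even 6MWD split, each scleroderma stratum holds about 45 × 0.15 = 7 patients, roughly 2 per arm.

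All of this stands and sets the severity. It does not explain why the strata are used for 6MWD and left out here.

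A reader might also infer that the relative risk will often be incalculable because one group has no events. At an assumed 10% risk the chance is 0.9^15 + 0.9^30 − 0.9^45 = 0.24, but at 40% it is about 0.6^15 = 0.0005. The documents give no rate that selects either. That problem is separate from stratification, and a Mantel-Haenszel relative risk would not cure it.

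**Conclusion.** The point holds in conditional form. The composite is tested without the strata that govern randomisation and the primary model. If the strata predict it, the 6-month chi-square is conservative: about 2 to 3 points of power lost at factor odds ratios of 3, 4 to 7 points at 5, and at most about 1 point at 2 or below. Event risks, stratum shares and factor effects are all assumptions, and the documents neither support nor exclude the upper end. Ignoring the strata does not inflate false positives, and the primary conclusion is not affected. Severity is minor. It is worth acting on because the change is nearly free and, if made before database lock, removes a later choice between adjusted and unadjusted results.

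**What to change.** In SAP 5.2 and Protocol 11.8:

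1. Make the 6-month test a CMH test over the randomisation strata.
2. Report a Mantel-Haenszel risk difference with 95% confidence interval beside the relative risk. The difference is still defined when one group has no events.
3. Stratify the log-rank test by the same factors.
4. Prespecify how sparse strata are collapsed, for example to PAH type alone.
5. Say which stratum value is used for patients stratified in error, since SAP 3.2 keeps them in the analysis.

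The cost is SAP and protocol wording and a small change to the SAS code, plus about 0.5 to 1.5 points of power if the strata turn out not to be prognostic.

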Secondary objectives with respect to pulmonary hemodynamics (i.e., PAP, cardiac output, RAP PAWP), quality of life, and other continuous secondary outcomes will be analyzed using an approach similar to that used for analysis of our primary outcome of 6MWD. The combined endpoint of death or clinical worsening of pulmonary arterial hypertension up to 12 months will be described using Kaplan-Meier plots and compared across the 3 study arms using log-rank tests. Chi square test statistics and relative risks with 95% confidence intervals will be used to determine the effect of four doses of treatment on the combined endpoint at 6 months (Arm 1 vs. Arms 2 and 3). The combined endpoint at 12 months in Arm 3 will be described using 95% confidence interval and compared to historical event rates.

Clinical worsening of pulmonary arterial hypertension will be defined by any of the following:

- 1. All-cause mortality
- 2. Hospitalization due to worsening cardiopulmonary status attributable to progression of disease
- 3. Decrease in 6MWD by $\geq 15\%$
- 4. Worsening of WHO functional class.

11.9. Analysis of Safety:

Safety endpoints related to the tolerability and safety of injection of the study product in patients with severe PAH will be divided into early and late endpoints.

Early (within 1 hour of each study product administration):

- Clinical evidence of allergic or other immune reaction that in the opinion of the investigator is possibly related to the cell product injection
- Evidence of pulmonary or systemic embolization
- Symptomatic hypotension
- A clinically significant drop in O₂ saturation.

Late (within 1 month [visits 0-2 and 6-8] or 3 months [visits 3 and 9] of study product delivery):

- Evidence of significant immune activation (i.e. increases in ESR, CRP)
- Evidence of new and more than mild right to left shunting (i.e. greater than grade 2 shunting) by semi-quantitative analysis on agitated saline contrast echocardiography; or new evidence of rapid appearance of contrast in the left atrium.

A safety analysis is planned after the first twelve participants complete primary endpoint data collection at the 6-month follow-up visit. Safety data will be sorted by treatment arms (blinded) to determine the distribution of potential safety concerns and be provided to the DSMB for review. The unblinded treatment allocation will be available from the statistician should the DSMB determine that a safety concern exists that necessitates unblinding.

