## 2.4 Framework

This will be a superiority trial, with primary aim to determine whether receiving a course of 4 monthly doses of eNOS-EPCs will improve the 6 minute walk distance (6MWD) at 6 months

compared to placebo. A minimally important mean difference of 50 meters was considered for this hypothesis.

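### The Month 6 test of death or clinical worsening needs a yes/no status for everyone and has no rule for participants lost event-free before Month 6; a log-rank and Kaplan-Meier analysis stopped at Month 6 is a cheap improvement

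*SAP*

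**What the plan says.** SAP 5.2 (Analysis of Additional Secondary Outcomes) and Protocol 11.8 give death or clinical worsening two comparative analyses.

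- **Month 6:** a chi-square test and relative risk with 95% CI for the effect of four doses "on the combined endpoint at 6 months (Arm 1 vs. Arms 2 and 3".
- **Month 12:** the endpoint "up to 12 months will be described using Kaplan-Meier plots and compared across the 3 study arms using log-rank tests".

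The components are death, hospitalization for disease progression, a fall in 6MWD of at least 15%, and a worse WHO class. From Month 6, Arm 1 receives cells (SAP 2.1).

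The intent-to-treat set is everyone randomized (SAP 3.3). SAP 2.3 raises the sample size "To account for 10% potential attrition". SAP 5.3 deals with missing data through general linear models. It adds a missing-not-at-random multiple imputation as a sensitivity analysis, without naming an endpoint.

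**The concern.** A chi-square and a relative risk need a yes or no for each participant analysed. Someone who leaves event-free at Month 2 has contributed two event-free months and has no Month 6 status. The plan does not say whether that person counts as event-free, counts as an event, or is left out. The likelihood approach in SAP 5.3 suits the continuous outcomes and supplies no rule for a chi-square.

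Secondary objective 10 asks for the effect at 6 months, and Months 0 to 6 are the only period that compares cells with placebo. With 15 against 30 participants, a few unclassified people can matter, and an unwritten coding choice could be made after the data are seen.

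**Working it through.** **1. The plan's own figure.** The documents give no event rate, power or sample size for this endpoint. The only figures are for 6MWD: "A total sample size of 39 participants (13 per arm"), 50 m, SD 85, correlation 0.80, two-sided 5%.

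- Residual SD = 85 × √(1 − 0.80²) = 51.0 m.
- Noncentrality = 50 / (51.0 × √(1/13 + 1/26)) = 2.89. The noncentral t on 35 df gives 80.1% power, so the stated 80% is reproduced.
- 39 / 0.90 = 43.3, rounded up to 44, then to 45 for three equal arms.

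Ten percent of 45 is 4.5 people.

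**2. Expected estimates by coding rule.** Assumptions: Month 6 risks of 40% (Arm 1, n = 15) and 20% (Arms 2+3, n = 30), so the true relative risk (RR) is 0.50 and the true risk difference (RD) 0.200. Event and loss times are exponential and independent. With risk p and loss d by Month 6, let L = −ln(1 − p) and M = −ln(1 − d).

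- Observed event: E = L/(L + M) × [1 − (1 − p)(1 − d)]
- Lost event-free: X = M/(L + M) × [1 − (1 − p)(1 − d)]
- Event-free coding uses E; exclusion uses E/(1 − X).

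Equal 10% loss:

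- Arm 1: E = 0.5108/0.6162 × 0.46 = 0.381.
- Arms 2+3: E = 0.2231/0.3285 × 0.28 = 0.190.
- Lost event-free: about 1.2 and 2.7 people.

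| Loss, Arm 1 / Arms 2+3 | RR, coded event-free | RR, excluded |
|---|---|---|
| 10% / 10% | 0.499 | 0.505 |
| 20% / 10% | 0.526 | 0.486 |
| 10% / 20% | 0.472 | 0.530 |
| 20% / 5% (10% overall) | 0.539 | 0.475 |
| 5% / 12.5% (10% overall) | 0.480 | 0.520 |
| 5% / 20% | 0.461 | 0.540 |
| 25% / 5% | 0.555 | 0.466 |

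With equal loss the RR is essentially unchanged. The RD becomes 0.191 if losses are coded event-free (about 5% smaller) and 0.205 if they are excluded. With unequal loss the two rules err in opposite directions.

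**3. Censored analysis.** Simulation with 15 vs 30, 4,000 runs per scenario and 10% loss in each group:

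| Assumed risks | Power, event-free | Power, excluded | Power, log-rank to Month 6 |
|---|---|---|---|
| 30% vs 15% | 21.6% | 22.7% | 23.4% |
| 40% vs 20% | 29.4% | 29.3% | 31.4% |
| 50% vs 25% | 37.8% | 38.0% | 41.4% |

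The gain is about 1 to 4 points here; a separate simulation gave 0 to 3. At 40% vs 20%, the mean Kaplan-Meier RD is 0.200 to 0.203 under 10/10, 20/10 and 10/20 loss.

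**4. Informative loss.** With assumed risks of 55% vs 23% and loss tied to each participant's event risk, the true RD was −0.318 and Kaplan-Meier gave −0.307. The true RR was 0.421; Kaplan-Meier gave 0.415 and both chi-square codings 0.418. Censoring does not cure this.

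**5. One dataset.** Suppose 7 events in Arm 1 and 6 in Arms 2+3, with 2 and 3 people lost (uncorrected chi-square):

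- Losses event-free: 7/15 vs 6/30, RR 0.43, p = 0.063.
- Losses excluded: 7/13 vs 6/27, RR 0.41, p = 0.045.
- Losses as events: 9/15 vs 9/30, RR 0.50, p = 0.053.

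The estimates are close, but the verdict at 5% changes with an unwritten rule.

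**The case against.** **Statuses can be recovered.** The premature withdrawal visit repeats 6MWD and WHO class, telephone follow-up or record review can reveal deaths and hospitalizations, and a registered letter seeks survival status (SAP 4.2). This stands in part. Participants may decline further contact, and a withdrawal visit at Month 2 does not give Month 6 status.

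**The 10% is for 6MWD.** A death leaves no walk distance but is an event here, so 10% lost event-free may be too high. This stands, and makes the equal-loss effect smaller still.

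**A fixed-time comparison is legitimate.** Two components are assessed at scheduled visits, and this is one of twelve secondary objectives tested without multiplicity adjustment. A one-sentence classification rule would close the bare gap. This also stands, so the point is an improvement and the planned test is not invalid.

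**Stronger readings to avoid.** A reader might infer that the chi-square necessarily shrinks the effect. The planned measure is the relative risk, which barely moves with equal loss and can move either way otherwise. A reader might also infer that this is the only analysis with placebo-controlled data. The 12-month curves cover Months 0 to 6, censor losses and can be read by arm at Month 6; what is missing is a formal comparison confined to those months with Arms 2 and 3 pooled. Nor does Kaplan-Meier solve the problem outright, since it assumes non-informative loss.

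**Conclusion.** The point holds as a modest, low-cost improvement. The only analysis confined to the placebo-controlled period cannot use partial follow-up, and no rule covers participants lost event-free before Month 6.

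At equal loss near 10% the consequence is small, against power that is low anyway: 17% to 39% with no loss, for assumed placebo risks of 20% to 50% and a true RR of 0.50. Unequal loss is the larger risk. The RR under event-free coding then runs from about 0.46 to 0.55, and the direction cannot be predicted in advance. The extremes of that range need marked imbalance; with overall loss held at 10%, the patterns shown give 0.480 to 0.539.

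All event rates and loss patterns are assumptions, because the documents give none for this endpoint.

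**What to change.** In SAP 5.2 and Protocol 11.8:

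- Make the Month 6 comparison of Arms 2+3 with Arm 1 a log-rank test. Report Kaplan-Meier risks, risk ratio and risk difference at Month 6, each with 95% CI.
- Censor at the Month 6 assessment, before the first Course 2 dose. Count events found at that assessment, and time visit-based events by nominal visit so that the ±5-day window does not exclude any. Censor lost participants at their last event-free contact.
- Keep the chi-square and relative risk as a sensitivity analysis, with losses coded once as event-free and once as events. This shows how far informative loss could move the result.
- Report the number of participants lost event-free before Month 6, by arm.

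Cost: wording in two documents. The data are already collected, and Kaplan-Meier and log-rank methods are already planned for this endpoint. The downside is a headline based on Kaplan-Meier risks instead of simple proportions.
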